9.3 Variables

The investigator collects historic data (demographic and clinical characteristics) from medical records if available, or else by interviewing the patient. Likewise, the investigator collects treatment related data during initial visit and follow-up visits. The investigator documents the study-relevant data for each patient in the case report form (CRF). The CRF is available upon request (see Table 3, Annex 1).

9.3.1 Variables to determine the primary endpoint(s)

The variable(s) for primary objective(s) is/are:

- Changes in pain, other symptoms, functions and knee related quality of life assessed KOOS in patients with knee OA from the first assessment throughout the observation period
- Changes in pain, others symptoms, functions and hip related quality of life assessed by HOOS in patients with hip OA from the first assessment throughout the observation period

9.3.2 Variables to determine the secondary endpoint(s)

The outcome variable(s) for secondary objective(s) is/are:

- Drug utilization of Theraflex® therapy as reported by the patient to their physician
- Patient satisfaction measured with a Likert response scale (from 1-very dissatisfied to 5 – very satisfied)
- Type, frequency and length of painkiller for the symptomatic treatment of hip OR knee OA for an observation period up to 64 weeks
- Other medical/physical therapy for OA related pain (drugs, duration of use, dose, frequency)

9.3.3 Detailed description of variables collected

9.3.3.1 Date of Visit

- Date (Day, Month, Year) of visit

9.3.3.2 Patient demographic data

For demographic/socio-demographic assessment, the following data will be recorded:

- Year of birth

- Age
- Gender
- Race (e.g. White, Black or African American, Asian, not reported)

9.3.3.3 Vital signs

Information on vital signs to be documented, (if such data are available and the collection of this data is the routine clinical practice of the Investigator) include:

- Temperature
- Blood pressure
- Heart rate

9.3.3.4 Physical Examination

Physical examination performed in accordance with routine clinical practice. Information on normal/abnormal findings after physical examination, height (at Visit 1 only) and weight. In the absence of the height meter and scale in the doctor's office.height and weight can be registered from the patient's words.

9.3.3.5 Lifestyle

- alcohol and tobacco use during the last 3 months prior to the visit

9.3.3.6 Disease history

Disease history describes any medical findings that are relevant to the underlying disease and were present before inclusion into the study. Findings and diagnosis meeting the criteria listed below have to be documented:

- Date of diagnosis
- Disease status at study start
- Risk factors, such as:
 - hereditary diseases of bones and joints
 - non-genetic (age, excess weight, hormonal disorders, malformations of the bones and joints, joint operations)
 - exogenous risk factors (professional activity, trauma, sports)

9.3.3.7 OA Classification according to Kellgren & Lawrence

The Kellgren and Lawrence system (Kellgren J.H., 1957 P. 494–501) is a method of classifying the severity of OA into five grades. Grade I to III as indicated in the label for Theraflex® is referring to this classification. In case it is normal clinical practice at the site to do the grading without using the Kellgren and Lawrence system, the subject can be still included in the study. Has the Kellgren Lawrence scale being used for the diagnosis?

Yes, if yes please indicate below which grade is diagnosed according to Kellgren and Lawrence:

- **grade 0:** no radiographic features of OA are present
- **grade 1:** doubtful joint space narrowing (JSN) and possible osteophytic lipping
- **grade 2:** definite osteophytes and possible JSN on anteroposterior weight-bearing radiograph
- **grade 3:** multiple osteophytes, definite JSN, sclerosis, possible bony deformity
- **grade 4:** large osteophytes, marked JSN, severe sclerosis and definite bony deformity

No

9.3.3.8 KOOS or HOOS questionnaire (PRO)

Depending on the diagnosis (knee vs. hip OA), one of the two following questionnaires will be used.

Knee injury and Osteoarthritis Outcome Score (KOOS)

The KOOS questionnaire should be completed during the visit at the physician by the patient.

KOOS consists of 5 subscales; Pain, other Symptoms, Function in daily living (ADL), Function in sport and recreation (Sport/Rec) and knee related Quality of life (QOL). The previous week is the time period considered when answering the questions. Standardized answer options are given (5 Likert boxes) and each question is assigned a score from 0 to 4.

KOOS has been validated in patients with mild to moderate OA (Kellgren and Lawrence grades I-III) of the knee hence a similar populations as observed in the study (Tanner, 2007).

KOOS is patient-administered, the format is user friendly, and takes about 10 minutes to complete.

The original KOOS Questionnaire contains a total of 42 questions. To reduce the number of questions to 27 the KOOS- physical short form (KOOS-PS) containing 7 Questions on function replaces the two subscales functions, daily living with 17 questions (A1-A17) and functions, sports and recreational activities with 5 questions (SP1-SP5).

The proposed questionnaire for the patient with knee OA would contain following elements therefore:

- Symptoms: 5 questions (S1-S5) from KOOS
- Stiffness: 2 Questions (S6- S7) from KOOS
- Pain: 9 Questions (P1-P9) from KOOS
- Function: 7 questions from KOOS-PS
- Quality of life: 4 Questions (Q1-Q4) from KOOS

Link for further information: <http://www.koos.nu/index.html>

Hip disability and Osteoarthritis Outcome Score (HOOS)

The HOOS questionnaire should be completed during the visit at the physician by the patient.

HOOS consists of 5 subscales; Pain, other Symptoms, Function in daily living (ADL), Function in sport and recreation (Sport/Rec) and hip related Quality of life (QOL). The last week is taken into consideration when answering the questions. Standardized answer options are given (5 Likert boxes) and each question gets a score from 0 to 4.

According to the user guidance published on their homepage, HOOS validation work is ongoing.

HOOS is patient-administered, the format is user friendly, and takes about 10 minutes to fill out. A Russian version of the questionnaire is not available.

The original HOOS Questionnaire contains a total of 40 questions. To reduce the number of questions to 24 the HOOS- physical short form (HOOS-PS) containing 5 Questions on function replaces the two subscales functions, daily living with 17 questions (A1-A17) and functions, sports and recreational activities with 4 questions (SP1-SP4)

- Symptoms: 3 questions (S1-S3) from HOOS
- Stiffness: 2 Questions (S4- S5) from HOOS
- Pain: 10 Questions (P1-P10) from HOOS
- Function: 5 questions from HOOS-PS
- Quality of life: 4 Questions (Q1-Q4) from HOOS

Link for further information: <http://www.koos.nu/index.html>

9.3.3.9 Patient satisfaction with Theraflex®

The Satisfaction question should be completed during the visit at the physician by the patient. Patient satisfaction measured with a Likert response scale (from 5 – very satisfied to 1-very dissatisfied).

How satisfied are you with your treatment with Theraflex® ?

- Very satisfied
- Satisfied
- Neither satisfied nor dissatisfied
- Dissatisfied
- Very dissatisfied

Guidance to the patients what the individual categories mean will be provided by the investigator.

9.3.3.10 Co-morbidities (medical history, concomitant diseases)

Co-morbidities are any medical findings, whether or not they pertain to the study indication, that were present before start of therapy with Theraflex® independent on whether or not they are still present. They have to be documented in the Medical History/Concomitant Diseases section.

For any co-morbidity, the diagnosis, the start and the stop date/ongoing have to be documented.

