9.2.7.3 Follow-up Visits I & II

Follow-up visit will be the first visit at the physician during the time frame week 16-24 (Follow-up I), week 36-44 (Follow-up II), after start of treatment with Theraflex®. If patient switches to another Symptomatic Slow-Acting drug in Osteoarthritis (SYSADOA), the observation of the patient is terminated.

During the follow-up visit the investigator conducts all examinations according to the local routine clinical practice. In addition the investigator provides to the subject the PRO

questionnaire and the overall satisfaction question for completion. The patient needs to assess the outcome of joint treatment, which was selected as the “target” at the first visit.

Following information will be captured in the CRF:

- Date of visit
 - day, month, year
- Physical Examination
- Weight (kg)
- Vital Signs
 - Blood Pressure
 - Body Temperature (axillary temperature)
 - Heart rate
- Review of Theraflex® drug utilization
 - Start / End of treatment
 - Dose/frequency of treatment
- KOOS or HOOS Questionnaire (PRO)
- Patient satisfaction with Theraflex®
- Concomitant medication
- Concomitant disease(s)
- Concomitant non- medication therapies (e.g. physiotherapy, surgery)
- Adverse events

All examinations are performed according to the local routine institutional practice as indicated by the attending physician. PRO should be completed at the time of the visit at the physician by the patient.

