9.2.7.4 Final Visit / End of Observation

Final Visit / End of Observation will be the first visit at the physician’s office after an observation period up to 64 weeks after start of treatment with Theraflex®. Final visit should be performed during the time frame week 56-64

During the visit the investigator conducts all examinations according to the local routine clinical practice. In addition the investigator provides to the subject the PRO questionnaire and the overall satisfaction question for completion. The patient needs to assess the outcome of joint treatment, which was selected as the target at the first visit.

Following information will be captured in the CRF:

- Date of visit
 - day, month, year
- Physical Examination
- Weight (kg)
- Vital Signs
 - Blood Pressure
 - Body Temperature (axillary temperature)
 - Heart rate
- Review of Theraflex® drug utilization

- Start / End of treatment
- Dose/frequency of treatment
- KOOS or HOOS Questionnaire (PRO)
- Patient satisfaction with Theraflex®
- Concomitant disease(s)
- Concomitant non-medication therapies (e.g. physiotherapy, surgery)
- Adverse events

All examinations are performed according to the local routine clinical practice as indicated by the attending physician. PRO should be completed at the time of the visit at the physician by the patient.

Premature end of therapy does not automatically imply end of documentation: the patient should be followed up until the end of the observation period (64 weeks) or until no longer possible.

Table 2: Tabulated overview on variables collected during the study

	Prior to inclusion to the study	Visit 1 Inclusion into the study	Visit 2 & 3 Follow-up visit	Visit 4 Final Visit / End of Observation
		First Visit after starting treatment with Theraflex® [not more than 2 weeks]	Week 16-24 Week 36-44 after start of treatment with Theraflex®	Week 56-64 after start of treatment with Theraflex®
Assessment of inclusion / exclusion criteria		X		
Information about the study	X			
Written Informed Consent		X		
Patient demographic data		X		
Physical Examination*		X	X	X
Height /Weight**		X	X	X
Vital signs		X	X	X
OA Staging according to Kellgren & Lawrence*		X		
Lifestyle		X		
Concomitant therapies other than drug		X	X	X
Medical history /concomitant diseases		X	X	X

Concomitant medication		X	X	X
Adverse events		X	X	X
Review of Theraflex® drug utilization		X	X	X
KOOS or HOOS Questionnaire (PRO)		X	X	X
Patient satisfaction (PRO)		X	X	X

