12.1 Definitions

An adverse event (AE) is any untoward medical occurrence in a patient administered a medicinal product and which does not necessarily have a causal relationship with this treatment. An AE can therefore be any unfavorable and unintended sign (e.g. an abnormal laboratory finding), symptom, or disease temporally associated with the use of a medicinal product, whether or not considered related to this medicinal product [9].

The term also covers laboratory findings or results of other diagnostic procedures that are considered to be clinically relevant (e.g. that require unscheduled diagnostic procedures or treatments or result in withdrawal from the study). The AE may be:

- A new illness
- Worsening of a sign or symptom of the condition under treatment or of a concomitant illness
- An effect of the study medication
- An effect of the comparator product
- Off label use, occupational exposure, lack of drug effect, medication error, overdose, drug abuse, drug misuse or drug dependency itself, as well as any resulting event
- An effect related to pre-existing condition improved (unexpected therapeutic benefits are observed)
- Product exposure via mother/ father (exposure during conception, pregnancy, childbirth and breastfeeding)

As mentioned above no causal relationship with a product is implied by the use of the term "adverse event".

An Adverse Reaction (AR) is defined as a response to a medicinal product which is noxious and unintended. An AR is any AE judged as having a reasonable suspected causal relationship to Theraflex®.

Causal relationship: The assessment of the causal relationship between an AE and the administration of treatment is a clinical decision based on all available information at the time of the completion of the CRF. The assessment is based on the question whether there was a "reasonable causal relationship" to the study treatment in question. Possible answers are "yes" or "no".

An assessment of "no" would include:

The existence of a clear alternative explanation (e.g. mechanical bleeding at surgical site)

Non-plausibility (e.g. the subject is struck by an automobile when there is no indication that the product caused disorientation that may have caused the event; cancer developing a few days after the first product administration)

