8.4. Concomitant diseases and medical conditions

All prior and concomitant diseases will be coded using the MedDRA dictionary (version 20.1 or later) according to the standard operating procedure of Data MATRIX LLC [4] and presented in separate tables by system organ class (SOC) and preferred term (PT).

Prior and concomitant diseases will be classified based on disease status at screening as recorded by investigators on the Medical History form in the CRF. Diseases with “Resolved” status will be considered as prior. Diseases having “Ongoing, positive dynamics”, “Ongoing, negative dynamics”, “Ongoing, no dynamics” status will be considered as concomitant.

Descriptive statistics for prior and concomitant diseases will reflect the number and percentage of patients with recorded diseases and relevant SOC and PT, as well as the number of these records. Patients with multiple diseases coded within the same SOC and PT will be counted only once within each SOC and PT. A patient may have multiple PTs within a SOC.

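### For illness starting between the first Theraflex dose and Visit 1 (0 to 2 weeks), the protocol and SAP disagree on whether it is co-morbidity or adverse event

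*Protocol*

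**What the plan says.** The plan sets the boundary between an existing condition and a later event in five places.

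- **Protocol 9.3.3.10** uses the start of treatment: "Co-morbidities are any medical findings, whether or not they pertain to the study indication, that were present before start of therapy with Theraflex". It adds: "For any co-morbidity, the diagnosis, the start and the stop date/ongoing have to be documented". An onset date is therefore collected.
- **Protocol 9.3.3.6**, which covers history relevant to the underlying disease, takes findings that "were present before inclusion into the study".
- **Protocol 12.2** starts AE documentation with the first intake following enrollment. Until Theraflex has been taken within the study, AEs and serious AEs need not be documented as such and count as medical history.
- **SAP 8.4** says: "Prior and concomitant diseases will be classified based on disease status at screening". The source is the Medical History form. A resolved disease is prior and any of three ongoing statuses is concomitant. The start date plays no part.
- **SAP Table 7.2:2**, for AEs with incomplete dates, decides what is treatment-emergent by comparison with the study drug start date.

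Protocol 9.2.7.2 allows Visit 1 up to 2 weeks after treatment start. In Protocol Table 2 the row "Medical history /concomitant diseases" is marked at every visit, next to a separate AE row. Protocol 12.1 counts a new illness as an AE, and also "Worsening of a sign or symptom of the condition under treatment or of a concomitant illness". SAP 10.2 builds the AE tables from the Adverse event form.

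**The concern.** A patient can enter this study only after buying and starting Theraflex, so any interval between first dose and Visit 1 is on-drug time that precedes enrollment. Two different boundaries enclose it: treatment start, and enrollment or screening. A condition that begins between them changes sides according to which section is followed.

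What is at stake is the table in which an on-drug illness appears. If it goes to the disease table, the AE tables omit an event from the opening days of the current course, and the baseline description contains something that was not there at baseline. Sites that read different sections could also handle identical events differently. The interval lies wholly within the first three weeks, which Protocol 9.3.3.11 asks to be recorded as a distinct dosing period.

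**Working it through.** The plan gives no figure to reproduce, so the check sets the rules side by side. The plan has no separate screening visit, and Protocol Table 2 puts the eligibility assessment at Visit 1. I therefore read screening in SAP 8.4 as Visit 1.

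Assumed case: first dose on day 1, new illness on day 5, Visit 1 on day 12 (12 − 1 = 11 days after start, inside the 14 allowed), illness still present.

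| Place | Cut-off used | Illness starting on day 5 |
|---|---|---|
| Protocol 9.3.3.10 | Theraflex start | Not a co-morbidity |
| Protocol 9.3.3.6 | Inclusion | Disease history, if relevant to the OA |
| Protocol 12.2 | First intake after enrollment | AE documentation not required; medical history |
| SAP 8.4 | Status at screening | Concomitant disease (prior, if resolved by day 12) |
| SAP Table 7.2:2 | Study drug start | Treatment-emergent, if on the AE form with an incomplete date |

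Following the collection rules in order:

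1. Protocol 12.2 places the illness in medical history.
2. SAP 8.4 takes it from the Medical History form and tabulates it as concomitant. Had it resolved by day 12, it would be labelled prior although it began on drug.
3. SAP 10.2 reads only the Adverse event form, so the illness does not enter the AE tables.
4. Protocol 9.3.3.10 says the record in step 2 should not be there. Table 7.2:2 would call the same event treatment-emergent if it had been put on the AE form.

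Protocol 9.3.3.6 adds a second mismatch. Section 9.3.3.10 covers findings whether or not they concern the study indication, so an OA-related finding falls under both sections, with two different cut-offs.

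Other onset times:

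- **Before the first dose:** all five places agree, and the condition is pre-existing.
- **After Visit 1 (say week 30):** Protocol 12.1 and 12.2 make a new or worsened illness an AE that must be documented. It has no status at screening, so SAP 8.4 gives it no category.

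Size of the interval: at most 2 weeks of up to 64, and 2 / 64 = 0.031, about 3% of observation time. This is a share of time and not of events. The documents give neither event rates nor the distribution of the gap between first dose and Visit 1.

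SAP 7.2 has rules for incomplete dates of therapies and of AEs, but none for diseases.

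**The case against.** The strongest reply is that section 12 already governs what is an AE, and from enrollment onward it does. The repeated disease item at Visits 2 to 4 might lead a reader to infer that illness arising at any time on treatment is diverted by design from the AE tables to the co-morbidity table. The documents do not support that. Sections 12.1 and 12.2 require such illness to be documented as an AE, AEs are a separate item at every visit, and SAP 8.4 is tied to screening status. The Visit 2 to 4 lists also drop the medical history item that Visit 1 has. Since 9.3.3.10 requires a stop date or ongoing status, updating known conditions is a natural reading of the repeat entry. Loss of a later event would need a site to file it only as a disease. What stands is that neither document says update only, and neither describes a reconciliation, so misfiling or double recording is unguarded.

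For the interval before Visit 1, three replies are possible.

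- **AEs are on the Visit 1 list.** A site might use that item for the day-5 illness. But 12.2 does not require it, and optional use would make sites differ.
- **The interval is short.** The study is descriptive, and neither table serves a primary or secondary endpoint. This limits the importance but does not remove the conflict.
- **Checks may exist elsewhere.** The CRF, Data Management Plan and Medical Review Plan were not available, so an existing edit check cannot be ruled out. A check would still need one agreed cut-off to work against.

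**Conclusion.** The point holds for onset after the first dose and before Visit 1. Protocol 9.3.3.10 and SAP Table 7.2:2 use treatment start, while Protocol 9.3.3.6, Protocol 12.2 and SAP 8.4 use inclusion, enrollment or screening. Followed as written, the plan tabulates an on-drug illness in this interval as a prior or concomitant disease and does not require it on the AE form. After Visit 1 there is only the lesser weakness of an unguarded second place to record an illness.

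The effect is confined to at most 2 weeks per patient and is nil for a patient seen on the day of starting. No number of patients or change in AE percentage can be derived from the documents. The conclusion assumes that screening means Visit 1 and that study drug start in the SAP means the first dose of the current Theraflex course. It is a modest inconsistency, worth correcting because it decides which table an early event enters.

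**What to change.** 1. **One cut-off.** Reconcile Protocol 9.3.3.6, 9.3.3.10 and 12.2 with SAP 8.4 on a single date. Section 12.2 must be part of this: a rule based on the first dose placed only in the SAP would contradict it.
2. **SAP 8.4.** Compare the recorded start date with the first Theraflex dose. Tabulate as co-morbidity only conditions with earlier onset, and list later onsets for reconciliation with the AE form. Add a rule to SAP 7.2 for incomplete disease start dates, and list records that cannot be placed.
3. **Visits 2 to 4.** State in Protocol 9.2.7.3, 9.2.7.4 and Table 2 that disease entries only update conditions already listed.

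The cost is a few sentences, minor programming on a date already collected, and some query work. AE counts may rise slightly. SAP version 2.0 is dated 13 July 2020, after the protocol's planned end of study in May 2020. If that timetable held, the protocol wording can no longer change what sites entered, but the SAP 8.4 date test and listing can still be applied to the final data.

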9.3.3.11 Drug Utilization

At every visit after start of the treatment with Theraflex® the physician should collect in detail start and end as well as frequency of Theraflex® treatment as reported by the patient into the CRF

To evaluate the drug utilization of the Theraflex® treatment the physician should also specifically ask how often Theraflex® is taken in average during a treatment.

- Start Date of Theraflex®
- End Date of Theraflex®
- Change of dosing/reason for change
- Dose
 - 3 capsules per Day
 - 2 capsules per Day
 - 1 capsules per Day

- The duration of the period without Theraflex®
The first three weeks which do have a different posology (3 capsules per day) according to the label should be entered as a distinct period to the treatment period with a recommended posology of 2 capsules per day.

